7.1.3 Allocation to Interventional Group

Participant randomization will be done by the UTHealth Houston Investigational pharmacy, from which we will be obtaining Estradiol and placebo. We will employ block randomization (with blocks size TBD to retain the blind), and randomization will be stratified by severity score at baseline.

7.2 Study Evaluations and Measurements

7.2.1 Baseline Evaluation

Baseline evaluations including:

- Trauma history
- Medical (including gynecological), psychiatric, and neurological history
- Characteristics (age, gender, race)
- Drug and medication use
- Life history such as any stressful life events
- Information regarding the subject's OCP use and associated menstrual cycle

7.2.2 Laboratory Evaluations

Approximately 18ml of blood will be drawn from each participant over the course of the study (see Table 1 below) using venipuncture. Hormone measures examined will include gonadal (total estrogens, estradiol and progesterone), hormones. The blood samples will be drawn and processed at LabCorp or Quest Diagnostics. If needed, due to scheduling constraints, blood may also be drawn by phlebotomist at UTHealth Houston and then processed by LabCorp/Quest Diagnostics. There are no plans to store any samples for prospective processing.

7.2.3 Urine Toxicology Screen and Saliva THC Test

If, on the day of any scanning visit, the participant's UTOX is positive for THC (and negative for all other substances), a saliva THC test will be administered in order to determine recency of THC use. If saliva THC test is negative; the scan will proceed as scheduled. If the saliva test is positive; the scan will be rescheduled. Saliva THC tests are rapid tests, with low participant burden, that can indicate recent THC use.

7.2.4 Pregnancy Testing

A urine pregnancy test will be performed for all female subjects. See section 7.2.5 for more detail.

7.2.5 fMRI Scans

Research subjects will undergo a 3T MRI scan during the second of the two experimental days at baseline and again at treatment endpoint. The MRI does include the use of experimental pulse sequences and/or RF coils. Some of the pulse sequences and/or RF coils are not FDA approved but are considered to pose no more than minimal risk.

Pregnancy Clause -- Although there are no known risks related to MRI on pregnant women or a fetus, there is a possibility of yet undiscovered pregnancy related risks. Since there is no possible benefit from participating in this protocol for a pregnant woman, we will exclude pregnant women. A negative urine pregnancy test will be required before a woman of child-bearing potential can participate in this study, and all participants will be on an oral contraceptive. Should a pregnancy be identified, a separate modification request including information on whether or not the pregnancy will be followed will occur.

7.2.6 Other Evaluations, Measures

Clinician Rated Measures

- MINI International Neuropsychiatric Interview for DSM-5 (MINI; Hergueta, Baker, & Dunbar, 1998)
- Clinician-Administered PTSD Scale for DSM-5 Past Month and Past Week versions (CAPS)
- Medical health: the general health form

- Gynecological/Menstrual history form
- Columbia Suicide Severity Rating Scale (C-SSRS; Posner et al., 2007)
- Clinical Global Impressions Severity and Improvement Scale (CGI-S; Guy 1976)
- Life Events Checklist Extended (LEC-5 Extended; Weathers et al., 2013)

Self-Rated Measures

- The Beck Depression Inventory (BDI-II: Beck et al., 1961) to quantify depressive symptoms
- The Beck Anxiety Inventory (Beck and Steer, 1990) to quantify general anxiety symptoms
- The Speilberger State Trait Anxiety Inventory (STAI: Spielberger, 1983) to quantify trait aspects of anxiety
- The Anxiety Sensitivity Index (ASI)
- Shock Expectancy Questionnaire
- Day-to-Day Experiences Form
- NEO-FFI-3-Short form (to assess big five dimensions of personality)
- Pittsburg Sleep Quality Index (PSQI)
- PTSD Diagnostic Scale for DSM-5 (PDS-5)
- Posttraumatic Cognitions Inventory (PTCI)
- Childhood Trauma Questionnaire (CTQ)
- Quality of Life Enjoyment and Satisfaction Questionnaire Short Form (Q-LES-Q-SF)

Safety Assessments:

All clinical visits and follow up assessments and experimental visits will include the following:

- Adverse Events (AE): clinicians/study team will track any adverse events that patients have experienced since their last visit. AEs will be documented and reviewed at all study visits.
- Concomitant Medications and Therapy: The study clinician will record the use of both study medication and concomitant medications on the Concomitant Medication log at each study visit. In addition any other psychosocial treatment will be recorded.
- Suicide Checklist: A modified CSSRS derived checklist to enable the clinician to assess, track and record any suicidal ideation, intent or behavior as part of the safety assessment.

Other Forms

- Demographics Form
- Edinburgh Handedness Survey
- Shock Expectancy Questionnaire
- Prior/Concomitant Medications Form
- Early Withdrawal Form

All study assessments and measures can be completed as written forms, filled out electronically using fillable PDFs, or completed by participants as surveys via the REDCap database system.

7.3 Study Schedule

TABLE 1: SCHEDULE OF STUDY PROCEDURES

Study Phase	Phone Screen	Screening/ Baseline Assessment	Experimental Days (I)		PE Session 1	PE Sessions 2-6	Experimental Days (II)		Post-Treatment Assessment	Follow-ups
Visit Number	n/a	1	2	3	4	5-9	10	11	12	13-14
Informed Consent		X								
Review Inclusion/Exclusion Criteria	X	X								
Demographics/Medical History		X								

Pregnancy Test		X	X	X			X	X		
Urine Toxicology Screen, Saliva THC test (if positive UTOX for THC on experimental/scanning days)		X	X	X			X	X		
Concomitant Medications and treatments	X	X			X	X			X	X
Blood Draw			X (or Visit 3)			X (at visit 5 and 9)	X (or Visit 11)			
Randomization				X						
Psychiatric evaluation measures		X	X	X	X	X	X	X	X	X
Estradiol/Placebo dosage						X				
Adverse Event / Unanticipated Problems Assessment		X	X	X	X	X	X	X	X	X
Habituation/Extinction Procedures			X				X			
Recall/Renewal Procedures				X				X		
PE Treatment Procedures					X	X				
Resting Skin Conductance					X	X				

TABLE 2: Schedule and list of evaluations and self-reports completed by participants.

Assessments Administered at Visit 1	Assessments Administered at PE Treatment Sessions	Assessments Administered at Experimental Visits	Assessments Administered at Post Treatment and Follow-ups
Clinician Administered Forms: LEC-5 Extended, MINI, CAPS-5 Past Month and Past Week versions, CGI-S, CSSRS (lifetime and recent)	Psychiatric Evaluation Measures: PDS-5, PTCI (PE Session 2, 4, and 6), BDI-II, Safety Assessments, Adherence Questionnaires	Shock Questionnaire, Speilberger State Trait Anxiety Inventory (STAI; state version / form Y1 only), AE Form	Clinician Administered Forms: CAPS-5 Past Week version, CAPS-5 Past Month version at 6-month follow-up only, MINI at 6-month f/u only, CGI-S, CSSRS (recent)
Psychiatric Evaluation Measures: CTQ, Beck Depression Inventory (BDI-II), Beck Anxiety Inventory, Speilberger State Trait Anxiety Inventory (STAI), Anxiety Sensitivity Index (ASI), Day-to-Day Experiences Form, NEO-Short Form, PSQI, PTCI, Quality of Life Enjoyment and Satisfaction Questionnaire Short Form (Q-LES-QSF), PDS-5		Pregnancy test, Urine Toxicology Test, Saliva THC Test (if UTOX is positive for THC)	Psychiatric Evaluation Measures: CTQ, Beck Depression Inventory (BDI-II), Beck Anxiety Inventory, Speilberger State Trait Anxiety Inventory (STAI), Anxiety Sensitivity Index (ASI), Day-to-Day Experiences Form, NEO-Short Form, PSQI, PTCI, Quality of Life Enjoyment and Satisfaction Questionnaire Short Form (Q-LES-QSF), PDS-5
MD/NP Administered Forms: Medical History/General Health Form, Gynecological History Form, Safety Assessments			MD/NP Administered Forms: Safety Assessments, Additional Treatment Inventory
Other Self-Rated Patient Forms: Edinburgh Handedness Survey, Demographics Form			
Pregnancy Test, Urine Toxicology Test			

7.3.1 **Procedures for Training of Clinicians in Prolonged Exposure (PE) Therapy**

Training Specific Aim: To train psychotherapists who will be involved in the main study to administer Prolonged Exposure (PE) therapy for posttraumatic stress disorder (PTSD) prior to the initiation of the main study.

Training Enrollment: Each clinician performing PE therapy on the study needs to pass on performance for 6 sessions of PE therapy for 2 eligible participants in order to receive their PE certification. If new clinicians are hired onto the study, more training participants will be recruited in order to certify these clinicians. We estimate this will take 2-3 participants treated per trainee. We also estimate a 50% screen fail rate on eligibility. Thus, we estimate that in total 25 participants will be enrolled in order to train 5 clinicians over the course of the study. These participants will only be included for training purposes and their data and participation will not contribute to the total participants included, or the analyses in the main part of the study

Consent for Training Participation: Participants will undergo a specific consent for the training protocol included in this submission. This consent will clarify the training aspects of the PE training and will not include the study medication or imaging components of the study (which will not be delivered to training participants). All other questionnaire assessments will be identical.

Recruitment and screening procedures, safety monitoring and post treatment referrals as needed for training participants will be identical to the procedures outlined in the main trial. Screening procedures will identify adults with a primary diagnosis of PTSD for whom treatment with PE is appropriate with the same entry criteria with the exception of concerns related to undergoing MRIs (e.g. metal implants) or testing estrogen. Thus the entry criteria for training participants is as follows:

Training Participant Inclusion Criteria

- Male or Female, 18-70 years of age
- Criterion A traumatic event
- At least one month post-trauma DSM-5 PTSD symptoms
- PDS-5 score ≥ 28
- Stable medications (for 3 or more months by the time of study entrance), with the exception of benzodiazepines). Benzodiazepine use will be excluded.
- Provide informed consent

Training Participant Exclusion Criteria

- Other primary diagnoses (e.g., pervasive developmental disorders, psychotic disorder, thought disorder, or presence of other disorder that is primary relative to PTSD symptoms)
- Imminent suicide risk in need of a higher level of care
- Concurrent trauma focused psychotherapy
- Pregnancy (to be ruled out by urine β -HCG).

Training procedures: Participants will receive the identical PE intervention described above with therapists being trained as approved study therapists. In addition, they will consent to videotapes of their therapy and assessment sessions being used for training purposes to certify the study therapist, as below.

TABLE 3: SCHEDULE OF TRAINING STUDY PROCEDURES

Study Phase	Screening	Baseline Assess	PE Session 1	PE Sessions 2-6
Visit Number	n/a	1	2	3-7
Informed Consent/Accent		X		
Review Inclusion/Exclusion Criteria	X	X		
Demographics/Medical History		X		

Pregnancy Test		X		
Urine Toxicology Screen		X		
Prior/Concomitant Medications	X	X		
Psychiatric evaluation measures		X		
Adverse Event / Unanticipated Problems Assessment		X	X	X
PE Treatment Procedures			X	X

Training protocol risks and discomforts are limited to those associated with assessments and PE therapy, with the addition of potential discomfort having sessions videotaped and reviewed by trainers.

Benefits include that training participants undergo expert diagnostic assessments and receive a gold standard psychotherapy treatment of PTSD at no cost. Prolonged Exposure is an evidence based first line treatment designed to reduce symptoms of PTSD.

Participants will receive free, evidence-based, first-line treatment for PTSD as part of the training study. Monetary compensation in the amount of \$100 will be provided to compensate for their time and any travel expenses. This amount will be given to participants upon completion of the PE therapy sessions.

Recording of Therapy Sessions:

All therapy sessions will be digitally video-recorded. This will allow us to 1) provide supervision for the clinicians, and 2) monitor the treatment and assessment information to be sure that we can evaluate whether the sessions are carried out according to the therapy guidelines. These recordings will be kept on an electronically secure, password protected hard drive in a locked room for no longer than 5 years. We will provide participants with a separate video consent form to review and complete.

People who will watch the recordings include the participant's study therapist and study-approved supervisors at UTHealth Houston and the University of Pennsylvania. Other study clinicians and/or people who are learning the study protocol may also hear some segments of the recording. Videos will be accessed only through secure channels that give access for viewing within the UTHealth Houston firewall.

Post-Endpoint:

Following the end of the treatment phase, patients interested in further treatment for residual PTSD symptoms will be given appropriate clinical referrals.

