5.2 Exclusion Criteria

An individual who meets any of the following criteria will be excluded from participation in this study:

1. Diagnosis of bipolar I disorder with a past year manic episode
2. Diagnosis of a psychotic disorder or psychotic symptoms that would interfere with the ability to focus on posttraumatic stress disorder (PTSD) in clinic, as determined by clinical judgment.
3. Diagnosis of moderate or severe substance use disorder that would interfere with the ability to focus on posttraumatic stress disorder (PTSD) in clinic, as determined by clinical judgment.
4. Cognitive impairment that would interfere with the ability to focus on posttraumatic stress disorder (PTSD) in clinic, as determined by clinical judgment.
5. History of neurological disease (that involves the brain), seizure, or significant head trauma (i.e., extended loss of consciousness, neurological sequelae, or known structural brain lesion).
6. Suicidal ideation with imminent risk that warrants a higher level of care.
7. Concurrent trauma focused psychotherapy
8. Pregnancy (to be ruled out by urine β -HCG).
9. Metallic implants or devices contraindicating magnetic resonance imaging by interfering with patient safety or fMRI data collection. Cases will be cleared by the Principal Investigator and/or Baylor College of Medicine (Imaging).
10. History of breast cancer or hormone-responsive cancer.
11. Use of benzodiazepines
12. Self-injurious behavior that involves suicidal intent, requires medical attention, or occurs daily.
13. High risk of adverse emotional or behavioral reaction, and/or an inability to understand study procedures or the informed consent process, based on investigator/clinician clinical evaluation (e.g., evidence of serious personality disorder, antisocial behavior, serious current stressors, lack of meaningful social support)

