5.3 Vulnerable Subjects

This study does not involve the enrollment of pregnant women, prisoners, employees, people with cognitive impairment or any decisional incapacity, fetuses, neonates or elderly or children under the age of 18.

Confidentiality for all study participants will be strictly adhered to. Only group level de-identified outcomes will be shared outside the study team and UTHealth Houston approved functions with access to clinical research participant level data (e.g. IRB, UTHealth Houston research pharmacy). All participants will undergo formal informed consenting in person (or online via Redcap) with an IRB approved clinical study investigator with as much time for questions as needed.

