In addition, any participants who have not improved at least 30% from their pre-treatment the 3-month follow-up CAPS-5 Past Week score and have a CAPS-5 Past Week score of 26 or greater at the 3-month follow-up will be offered additional treatment if they wish. Participants will then have the option to receive up to 4 additional sessions of PE delivered for an hour a week (for a total number of 10 sessions of PE) immediately following the 3-month follow-up visit. All participants will receive safety assessments throughout the study and at 3 and 6 month follow ups, and will be assisted with clinical referrals if desired and/or indicated.

Monitoring of Mental Status and Mood. Subjects' mental status will be closely monitored throughout the course of the study. As previously stated, it is not uncommon for treatment of trauma-related symptoms to be associated with temporary exacerbation in participants' symptoms of PTSD and depression. However, some participants may experience symptom exacerbations or psychiatric emergencies that require treatment beyond that provided by the study. In all cases, the client's mental status will be the utmost priority and immediate action will be taken to provide appropriate care. The intake evaluation for the study will include the Columbia-Suicide Severity Rating Scale to adequately assess suicide risk before study enrollment, and study therapists will routinely evaluate mood over the course of treatment, including the presence or absence of suicidal thoughts (using the BDI-II followed by clinical interview with a modified suicide check list at each

visit), and if any suicidal thoughts, plans or actions are present, these will be dealt with using the detailed plan outlined in Protection against Suicidality in the section immediately below.

Management of Suicide Risk

Several strategies will be implemented to assist in early identification and appropriate management of suicide risk. This protocol will utilize the Columbia Suicide Scale (C-SSRS) at screening and a suicide check list at each clinical and psychiatric assessment follow up visit to routinely assess suicidal ideation, impulses and behaviors. In addition, the BDI will be completed and reviewed by the study therapist who will be working closely with each participant.

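### The training-phase entry list in section 7.3.1 does not follow its own stated rule: three main-trial exclusions are absent and three narrowed, and Table 3 omits checks promised at therapy sessions

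*Combined protocol and SAP*

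**What the plan says.** Section 7.3.1 describes a separate group of volunteers who receive the trial's six-session PE course, without study drug or imaging, so that therapists can be certified. A therapist must pass on two such cases before certification. Recruitment, screening and safety monitoring are to match the main trial. Volunteers are to be adults whose primary diagnosis is PTSD and for whom PE is suitable, "with the same entry criteria with the exception of concerns related to undergoing MRIs (e.g. metal implants) or testing estrogen". The list is then presented as a consequence of that sentence: "Thus the entry criteria for training participants is as follows".

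The listed inclusion criteria are "Male or Female, 18-70 years of age", a Criterion A event, PTSD symptoms at least a month after the trauma, PDS-5 of at least 28, stable medication without benzodiazepines, and consent. The listed exclusions are another diagnosis that is primary, imminent suicide risk, concurrent trauma-focused therapy, and pregnancy.

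The main trial has 13 exclusions in section 5.2. Among them are item 4, "Cognitive impairment that would interfere with the ability to focus"; item 12, "Self-injurious behavior that involves suicidal intent, requires medical attention, or occurs daily"; and item 13, "High risk of adverse emotional or behavioral reaction, and/or an inability to understand study procedures or the informed consent process". Section 5.3 adds that the study does not enroll "people with cognitive impairment or any decisional incapacity, fetuses, neonates or elderly".

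On monitoring, the consent paragraph of section 7.3.1 says that, apart from drug and imaging, the questionnaires are the same as in the main trial. Section 7.2.6 places adverse events, concomitant medications and a suicide checklist at all clinical visits. Section 8.1 has therapists follow mood "using the BDI-II followed by clinical interview with a modified suicide check list at each" visit.

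**The concern.** A rule and the list derived from it should agree. Here staff who screen by the rule and staff who screen by the list would reach different decisions on some volunteers, and nothing in the section says which governs.

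The direction of the difference matters. The training group receives the same exposure therapy as the randomized group, but from therapists who have not yet passed certification. Several main-trial safeguards that have nothing to do with scanning or estrogen are weaker or missing for that group. Section 8.1 says exposure is meant to provoke an emotional reaction and that therapists are to be trained in titrating it, so criteria on self-injury and on reaction risk are relevant to these sessions. If staff also work from Table 3, some between-session checks that the text relies on would not be prompted.

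**Working it through.** There is no power or error-rate figure to reproduce. The check compares the sections line by line, with one count for scale.

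**Step 1. Section 5.2 against the training list in section 7.3.1.**

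| Section 5.2 item | In the training list | Explained by the MRI or estrogen exception? |
|---|---|---|
| 6 imminent suicide risk | kept | not needed |
| 7 concurrent trauma-focused therapy | kept | not needed |
| 8 pregnancy | kept | not needed |
| 11 benzodiazepines | kept, within the inclusion criteria | not needed |
| 9 metal implants | dropped | yes |
| 10 hormone-responsive cancer | dropped | yes |
| 5 neurological disease, seizure, head trauma | dropped | arguably; not counted here |
| 4 cognitive impairment | absent | no |
| 12 self-injury | absent | no |
| 13 reaction risk or inability to understand procedures or consent | absent | no |
| 1 bipolar I, recent mania | only if primary over PTSD | no |
| 2 psychosis | only if primary over PTSD | no |
| 3 substance use disorder | only if primary over PTSD | no |

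Tally: 4 kept + 2 dropped as the exception allows + 1 arguable + 3 absent + 3 narrowed = 13. The unexplained differences are 3 + 3 = 6 of 13.

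**Step 2. Diagnosis.** The introductory sentence requires PTSD as the primary diagnosis. The list requires symptoms and a PDS-5 threshold; section 7.2.6 classes the PDS-5 as self-rated. The main trial requires a full or subPTSD diagnosis and a CAPS-5 Past Month score of at least 20 (section 5.1). So the list matches neither its own introduction nor section 5.1, and the exception does not explain the gap.

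**Step 3. Schedule.**

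| Check | Main trial at PE sessions | Table 3 (training) |
|---|---|---|
| Psychiatric measures, including BDI-II | marked in Table 1; BDI-II named in Table 2 | baseline only |
| Concomitant medications | marked in Table 1; required by section 7.2.6 | screening and baseline only |
| Suicide checklist | sections 7.2.6 and 8.1; Table 2 lists safety assessments | no entry |
| Adverse events | marked in Table 1 | marked at every session |

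**Step 4. Scale.** Section 7.3.1 gives 5 clinicians, 2 to 3 participants treated per trainee, and a 50% screen-failure rate.
- Treated: 5 × 2 = 10 to 5 × 3 = 15.
- Enrolled: 10 / 0.5 = 20 to 15 / 0.5 = 30. The midpoint, 5 × 2.5 / 0.5 = 25, reproduces the plan's figure of 25.

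The 25 is therefore an enrollment figure that includes screen failures. The number exposed to treatment by trainees is about 10 to 15.

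**The case against.** The strongest reply is that other text already protects these volunteers. Imminent suicide risk remains an exclusion. Screening looks for people for whom PE is suitable, which leaves room for clinical judgment, and items 3, 4 and 13 of section 5.2 rest largely on such judgment anyway. Section 5.3 rules out cognitive impairment and decisional incapacity, and section 12.3.1 requires competence to consent, which covers part of item 13. Sessions are recorded and supervised, and section 8.1 puts clinical supervisors on call. All of this stands and lowers the risk. It does not supply a listed ground for excluding someone under item 12 or under the reaction-risk part of item 13. Section 5.2 lists self-injury separately from imminent suicidal ideation, so keeping the latter does not stand in for the former.

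On Table 3, it is fair to say that Table 1 has no separate row for the suicide checklist either, and that the text makes monitoring identical. But Table 1 does mark psychiatric measures and medication review at PE sessions, and Table 3 marks neither there.

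Several stronger readings are tempting. A reader might infer that a person with daily self-injury or a recent manic episode is eligible for training treatment; the documents show only that such a person is not expressly excluded by the list, since the suitability sentence and the primary-disorder exclusion still apply. A reader might count items 1 and 3 as missing; they are narrowed, and item 2 is narrowed in the same way. A reader might set 25 training participants against 80 randomized, but those figures have different denominators. A reader might object to men, to ages up to 70, or to certifying therapists on a population unlike the trial's. Sex and age can plausibly follow from not testing estrogen, section 5.3 does not define the age term it uses, and the choice of certification population contradicts nothing in the plan.

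**Conclusion.** The inconsistency is real and can be confirmed by reading sections 5.2 and 7.3.1 together. Six of 13 exclusions differ in ways the stated exception does not explain: three absent and three narrowed. Items 12 and 13 are the clearest, because no other listed criterion fully covers them. The diagnostic requirement and Table 3 each conflict with neighboring text as well.

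The count assumes that item 5 belongs under the MRI exception; if it does not, the count becomes 7. The 10 to 15 people treated rests on the plan's own estimates and would grow if more therapists are hired. Section 7.3.1 keeps training data out of the main analyses, so the trial's inference is untouched. The matter concerns participant safety and protocol consistency, in a small group with several partial safeguards. It should be corrected, at modest priority.

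**What to change.** Reconcile the introductory sentence and the list in section 7.3.1 with sections 5.2 and 5.3, taking items 12 and 13 first, then items 4 and 1 to 3, then the diagnostic requirement. Either the list should follow the stated rule, or the rule should be reworded and each departure stated and justified to the IRB. Reconcile Table 3 with the text of section 7.3.1, with sections 7.2.6 and 8.1, and with Tables 1 and 2, so that the schedule and the text show the same checks at therapy sessions. Which clinical criteria and checks should apply is for the investigators and the IRB.

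The cost is a wording amendment and its IRB review. The interview, forms and checklist already exist in the protocol. If the list is brought into line with the rule, some further volunteers may be screened out, and the 50% screen-failure estimate behind the figure of 25 should then be looked at again.
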